16.11 Appendix 11: Liver event and laboratory trigger definitions and follow-up requirements

Table 16-4 Liver Event and Laboratory Trigger Definitions

	Definition/ threshold
LIVER LABORATORY TRIGGERS	$3 \times \text{ULN} < \text{ALT} / \text{AST} \leq 5 \times \text{ULN}$ $1.5 \times \text{ULN} < \text{TBL} \leq 2 \times \text{ULN}$
LIVER EVENTS	$\text{ALT or AST} > 5 \times \text{ULN}$ $\text{ALP} > 2 \times \text{ULN}$ (in the absence of known bone pathology) $\text{TBL} > 2 \times \text{ULN}$ (in the absence of known Gilbert syndrome)

ALT or AST > 3 × ULN and INR > 1.5
Potential Hy's Law cases (defined as ALT or AST > 3 × ULN and TBL > 2 × ULN [mainly conjugated fraction] without notable increase in ALP to > 2 × ULN)
Any clinical event of jaundice (or equivalent term)
ALT or AST > 3 × ULN accompanied by (general) malaise, fatigue, abdominal pain, nausea, or vomiting, or rash with eosinophilia
Any adverse event potentially indicative of a liver toxicity *

* These events cover the following: hepatic failure, fibrosis and cirrhosis, and other liver damage-related conditions; non-infectious hepatitis; benign, malignant and unspecified liver neoplasms

TBL: total bilirubin; ULN: upper limit of normal

Table 16-5 Follow up Requirements for Liver Events and Laboratory Triggers

Criteria	Actions required	Follow-up monitoring
Potential Hy's Law case ^a	Discontinue the study drug immediately Hospitalize, if clinically appropriate Establish causality Complete liver eCRF	ALT, AST, TBL, Alb, PT/INR, ALP and γGT until resolution ^c (frequency at investigator discretion)
ALT or AST		
> 8 × ULN	Discontinue the study drug immediately Hospitalize if clinically appropriate Establish causality Complete liver eCRF	ALT, AST, TBL, Alb, PT/INR, ALP and γGT until resolution ^c (frequency at investigator discretion)
> 3 × ULN and INR > 1.5	Discontinue the study drug immediately Hospitalize, if clinically appropriate Establish causality Complete liver eCRF	ALT, AST, TBL, Alb, PT/INR, ALP and γGT until resolution ^c (frequency at investigator discretion)
> 5 to ≤ 8 × ULN	Repeat LFT within 48 hours If elevation persists, continue follow-up monitoring If elevation persists for more than 2 weeks , discontinue the study drug Establish causality Complete liver eCRF	ALT, AST, TBL, Alb, PT/INR, ALP and γGT until resolution ^c (frequency at investigator discretion)

Criteria	Actions required	Follow-up monitoring
> 3 × ULN accompanied by symptoms ^b	Discontinue the study drug immediately Hospitalize if clinically appropriate Establish causality Complete liver eCRF	ALT, AST, TBL, Alb, PT/INR, ALP and γGT until resolution ^c (frequency at investigator discretion)
> 3 to ≤ 5 × ULN (patient is asymptomatic)	Repeat LFT within the next week If elevation is confirmed, initiate close observation of the patient	Investigator discretion Monitor LFT within 1 to 4 weeks
ALP (isolated)		
> 2 × ULN (in the absence of known bone pathology)	Repeat LFT within 48 hours If elevation persists, establish causality Complete liver eCRF	Investigator discretion Monitor LFT within 1 to 4 weeks or at next visit
TBL (isolated)		
> 2 × ULN (in the absence of known Gilbert syndrome)	Repeat LFT within 48 hours If elevation persists, discontinue the study drug immediately Hospitalize if clinically appropriate Establish causality Complete liver eCRF	ALT, AST, TBL, Alb, PT/INR, ALP and γGT until resolution ^c (frequency at investigator discretion) Test for hemolysis (e.g., reticulocytes, haptoglobin, unconjugated [indirect] bilirubin)
> 1.5 to ≤ 2 × ULN (patient is asymptomatic)	Repeat LFT within the next week If elevation is confirmed, initiate close observation of the patient	Investigator discretion Monitor LFT within 1 to 4 weeks or at next visit
Jaundice	Discontinue the study drug immediately Hospitalize the patient Establish causality Complete liver eCRF	ALT, AST, TBL, Alb, PT/INR, ALP and γGT until resolution ^c (frequency at investigator discretion)
Any AE potentially indicative of a liver toxicity*	Consider study drug interruption or discontinuation Hospitalization if clinically appropriate Establish causality Complete liver eCRF	Investigator discretion

* These events cover the following: hepatic failure, fibrosis and cirrhosis, and other liver damage-related conditions; non-infectious hepatitis; benign, malignant and unspecified liver neoplasms

TBL: total bilirubin; ULN: upper limit of normal

^a Elevated ALT/AST > 3 × ULN and TBL > 2 × ULN but without notable increase in ALP to > 2 × ULN

^b (General) malaise, fatigue, abdominal pain, nausea, or vomiting, or rash with eosinophilia

Criteria	Actions required	Follow-up monitoring
° Resolution is defined as an outcome of one of the following: (1) return to baseline values, (2) stable values at three subsequent monitoring visits at least 2 weeks apart, (3) remain at elevated level after a maximum of 6 months, (4) liver transplantation, and (5) death.		

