9.1 Discontinuation

9.1.1 Discontinuation of study treatment

Discontinuation of study treatment for a subject occurs when study treatment is stopped earlier than the protocol planned duration and can be initiated by either the subject or the investigator.

The investigator must discontinue study treatment for a given subject if, he/she believes that continuation would negatively impact the subject's well-being.

The following circumstances **require** study treatment discontinuation:

- Withdrawal of informed consent
- Emergence of the following adverse events:
 - a. Any severe or serious adverse event that is not compatible with administration of study medication, including adverse events that require treatment with an unacceptable co-medication
 - b. Onset of lymphoproliferative disease or any malignancy except for treated basal cell carcinoma, treated actinic keratoses, treated *in situ* carcinoma of the cervix or non-invasive malignant colon polyps which are being or have been removed
 - c. Life-threatening infection
 - d. Severe hypersensitivity reaction or anaphylactic reaction
- Any laboratory abnormalities that in the judgment of the investigator are clinically significant and are deemed to place the subject at a safety risk for continuation in the study (A general guidance on clinically notable laboratory values is provided in [Appendix 1](#)).
- Pregnancy
- Use of any biologic immunomodulating agent except secukinumab
- Any protocol deviation that results in a significant risk to the subject's safety

In addition to these requirements for study treatment discontinuation, the investigator should discontinue study treatment for a given subject if there is a lack of improvement or worsening of their symptoms, or if on balance, he/she thinks that continuation would be detrimental to the subject's well-being.

If discontinuation of study treatment occurs, the investigator should make a reasonable effort to understand the primary reason for the subject's premature discontinuation of study treatment and record this information.

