10.2 Additional Safety Monitoring

10.2.1 Liver safety monitoring

To ensure subject safety and enhance reliability in determining the hepatotoxic potential of an investigational drug, a standardized process for identification, monitoring and evaluation of liver events has to be followed.

The following two categories of abnormalities / adverse events have to be considered during the course of the study (irrespective of whether classified/reported as AE/SAE):

- Liver laboratory triggers, which will require repeated assessments of the abnormal laboratory parameter
- Liver events, which will require close observation, follow-up monitoring and contributing factors will be recorded in the CRF as AEs with contributing factors captured as concomitant medication or procedures as appropriate

Please refer to [Table 16-4](#) in [Appendix 16.11](#) for complete definitions of liver laboratory triggers and liver events.

Every liver event defined in [Appendix 16.11](#), [Table 16-4](#) should be followed up by the investigator or designated personnel at the trial site, as summarized below. Additional details on actions required in case of liver events are outlined in [Table 16-5](#). Repeat liver chemistry tests (i.e. ALT, AST, TBL, PT/INR, ALP and G-GT) to confirm elevation.

- These liver chemistry repeats will be performed using the central laboratory. If results will not be available from the central laboratory, then the repeats can also be performed at a local laboratory to monitor the safety of the subject. If a liver event is subsequently reported, any local liver chemistry tests previously conducted that are associated with this event should have results recorded on the appropriate CRF
- If the initial elevation is confirmed, close observation of the subject will be initiated, including consideration of treatment interruption if deemed appropriate.
- Discontinuation of the investigational drug (refer to the Discontinuation of study treatment section), if appropriate
- Hospitalization of the subject if appropriate
- Causality assessment of the liver event
- Thorough follow-up of the liver event should include
 - These investigations can include based on investigator's discretion: serology tests, imaging and pathology assessments, hepatologist's consultancy; obtaining more detailed history of symptoms and prior or concurrent diseases, history of concomitant drug use, exclusion of underlying liver disease

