16.1 Appendix 1: Clinically notable laboratory values

The following criteria will be used to define expanded limits and notable abnormalities of key laboratory tests.

Clinically notable values will be forwarded to Novartis at the same time that they are sent to investigators. Any action based on these laboratory values should be discussed with Novartis personnel.

Table 16-1 Safety Analyses: Expanded Limits and Notable Criteria

		Notable Criteria	
Laboratory Variable		Standard Units	SI Units
LIVER FUNCTION AND RELATED VARIABLES			
SGOT (AST)		>3 x ULN	>3 x ULN
SGPT (ALT)		>3 x ULN	>3 x ULN
Bilirubin		>2 x ULN	>2 x ULN
Alkaline phosphatase		>2.5 x ULN	>2.5 x ULN
RENAL FUNCTION, METABOLIC AND ELECTROLYTE VARIABLES			
Creatinine (serum)		>2 x ULN	>2 x ULN

HEMATOLOGY VARIABLES

Hemoglobin: 20 g/L decrease from baseline

Platelet count: <100x10E9/L

White blood cell count: <0.8 x LLN

Neutrophils: <0.9 x LLN

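### Table 16-5 can give a patient with bilirubin and ALP both above 2×ULN a weaker stopping rule than a patient with raised bilirubin alone

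*Protocol*

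**What the plan says.** Protocol Section 10.2.1 calls for a standardized process for liver events. It takes the definitions from Table 16-4 and points to Table 16-5 for the required actions, both in Appendix 11 (Section 16.11).

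- **Table 16-4** lists TBL > 2×ULN ("in the absence of known Gilbert syndrome") and ALP > 2×ULN (without known bone pathology) as liver events. Neither entry requires the elevation to be isolated.
- **Table 16-5, potential Hy's Law row:** immediate stop. Footnote a gives the condition as "Elevated ALT/AST > 3 × ULN and TBL > 2 × ULN but without notable increase in ALP to > 2 × ULN".
- **Table 16-5, TBL > 2×ULN row**, under a heading limited to isolated elevations: repeat within 48 hours, then "If elevation persists, discontinue the study drug immediately".
- **Table 16-5, ALP > 2×ULN row**, also limited to isolated elevations: repeat within 48 hours and establish causality. It contains no stop.
- **Table 16-5, ALT/AST > 3 to ≤ 5×ULN, asymptomatic:** "Repeat LFT within the next week If elevation is confirmed, initiate close observation of the patient". It contains no stop.
- **Table 16-5, ALT/AST > 5 to ≤ 8×ULN:** repeat within 48 hours, then "If elevation persists, continue follow-up monitoring", with a stop only after more than 2 weeks of persistence.
- **Immediate stops whatever the ALP:** ALT/AST > 8×ULN, ALT/AST > 3×ULN with INR > 1.5 or with footnote b symptoms, and clinical jaundice.

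The protocol does not define *isolated*, and no rule says which row prevails when several match.

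**The concern.** A stopping table should not become more lenient as liver tests get worse. Here the addition of a raised ALP removes a patient from the Hy's Law row, and the *isolated* heading can keep that patient out of the bilirubin row. What is left is the ALT/AST row, or no numeric row at all. The exclusion of raised ALP from the Hy's Law definition is conventional and is not disputed. The difficulty is that the excluded patients have no row of their own and can fall below the action for bilirubin alone.

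The SAP's note to its Table 2-6 (Section 2.7.2) recognises that ALT/AST > 3×ULN with TBL > 2×ULN and ALP ≥ 2×ULN can still turn out to be severe drug-induced liver injury. The stake is further infusions of study drug to a patient with that pattern, and different handling of identical results by different sites.

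**Working it through.** The plan gives no figure to reproduce, so the check applies the rows of Table 16-5 as written.

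**Inputs.** All thresholds and actions come from Table 16-5 and its footnotes. The patient is asymptomatic, with INR ≤ 1.5, no jaundice, no known Gilbert syndrome and no known bone pathology.

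**Readings of *isolated*.** Strict: no other listed liver test is above its table threshold. Lenient: ALT/AST is not above 3×ULN.

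**Ranking of stops, weakest to strongest.** None < after more than 2 weeks < if persistent at the 48-hour repeat < immediate.

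**Step 1: worked cases, all with TBL 2.5×ULN.** The reference is TBL 2.5 alone (ALT 1, ALP 1), which is stopped if it persists at 48 hours.

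| ALT (×ULN) | ALP 1×ULN | ALP 2.5×ULN, strict | ALP 2.5×ULN, lenient |
|---|---|---|---|
| 1 | stop if persistent at 48 h | no numeric row | stop if persistent at 48 h |
| 4 | immediate (Hy's Law) | observe, no stop | observe, no stop |
| 6 | immediate (Hy's Law) | stop after > 2 weeks | stop after > 2 weeks |
| 9 | immediate | immediate | immediate |

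At ALT 4 and ALT 6 the action is weaker than the reference under both readings. At ALT 1 it is weaker only under the strict reading.

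**Step 2: all patterns.** There are 4 ALT/AST bands (≤ 3, > 3–5, > 5–8, > 8), 3 TBL bands (≤ 1.5, > 1.5–2, > 2) and 2 ALP bands (≤ 2, > 2). That gives 4 × 3 × 2 = 24 patterns, less the all-normal one = 23. Each was compared with the action for each of its abnormalities taken alone.

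| Reading | Weaker stop | Weaker only in repeat timing, causality assessment or eCRF |
|---|---|---|
| Strict | 3 | 3 |
| Lenient | 2 | 2 |
| *Isolated* deleted, most stringent row applied | 0 | 0 |

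The strict weaker stops are TBL > 2 and ALP > 2 with ALT/AST ≤ 3, > 3–5 or > 5–8. The lenient reading removes the first. The strict non-stop differences are ALT/AST ≤ 3 with TBL > 1.5–2 and ALP > 2, and ALT/AST > 3–5 with ALP > 2 at TBL ≤ 1.5 or > 1.5–2. The lenient reading again removes the first.

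**Step 3: what it means for dosing.** Infusions are four-weekly (Section 6.1.3), so 28 days apart. Suppose the abnormal sample is drawn at an infusion visit. At ALT/AST > 5 to ≤ 8×ULN, the stop after more than 14 days still falls before the next dose at day 28, so the difference is mainly timing. At > 3 to ≤ 5×ULN the table sets no stop before the next or any later infusion.

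**The case against.** The strongest reply is that the patient is not left unmanaged. Section 9.1.1 requires discontinuation for "Any laboratory abnormalities that in the judgment of the investigator are clinically significant and are deemed to place the subject at a safety risk". Section 10.2.1 applies to every Table 16-4 liver event, which includes TBL > 2×ULN, and lists repeat tests, close observation, consideration of interruption and "Discontinuation of the investigational drug (refer to the Discontinuation of study treatment section), if appropriate". Appendix 1 (Section 16.1) makes ALT/AST > 3×ULN, bilirubin > 2×ULN and ALP > 2.5×ULN notable values sent to the sponsor, and adds "Any action based on these laboratory values should be discussed with Novartis personnel". The last row of Table 16-5 asks the site to consider interruption or discontinuation for any adverse event suggesting liver toxicity. All of this stands, but every one of these provisions depends on judgement. None corrects the fixed rule.

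Second, *isolated* might mean only that the case is not a Hy's Law case, in which event the TBL row catches everyone and nothing is inverted. That is possible, but three raised liver tests are hard to call an isolated bilirubin rise, and the hemolysis test in that row points to a narrower meaning.

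Third, raised ALP may indicate gall bladder or bile duct obstruction, as the SAP note says, so leaving mixed patterns to clinical judgement is defensible. The same note keeps severe drug injury open, and clinical choice does not explain a lower required action than for bilirubin alone.

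Fourth, the scope is narrow. Fatigue, malaise, nausea, vomiting or abdominal pain with ALT/AST > 3×ULN already triggers an immediate stop. Exclusion criterion 13 keeps out patients with any liver parameter above 2×ULN or bilirubin above 1.6 mg/dL at entry. The count of 23 patterns describes the table and says nothing about how often patients fall into each cell. These limits are correct, and they bear on how much the point matters.

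**Conclusion.** The concern holds. Followed literally, Table 16-5 gives a weaker stop than for TBL > 2×ULN alone in 3 of 23 patterns (strict reading) or 2 of 23 (lenient). The case that matters most is ALT/AST > 3 to ≤ 5×ULN with TBL and ALP both > 2×ULN, where the table requires observation only under either reading. With ALT/AST ≤ 3×ULN there is a gap only under the strict reading.

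The result assumes no symptoms, no jaundice, INR ≤ 1.5, and that *isolated* restricts the row in one of the two ways set out. The documents give no frequency for the pattern. I expect few of the approximately 380 patients to be affected and a negligible effect on the primary endpoint. The change should be made for subject safety and for consistent handling across sites.

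**What to change.** Delete the *isolated* qualifier from the TBL and ALP rows of Table 16-5, and add one sentence: when more than one row applies, the most stringent action governs. The Hy's Law row can stay as it is.

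An alternative is a new row for TBL > 2×ULN with ALP > 2×ULN at any ALT/AST, with an action at least as strong as for TBL > 2×ULN alone, plus the same sentence. This removes the weaker stops. It leaves the non-stop differences, because all of those have TBL ≤ 2×ULN. Deletion is therefore the better option.

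The cost is a short wording amendment to one appendix table and possibly a few more treatment stops. A stop before Week 16 counts as non-response under the composite variable in Section 12.4.1, but the numbers should be too small to matter. No new assessment is needed, since ALT, AST, TBL and ALP are already in the follow-up panel.

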16.12 Appendix 12: Guidelines for administering the PRO questionnaires

Before trial start

Study coordinators should familiarize themselves with the PRO questionnaire(s) in the trial and identify any items where a subject's response might highlight issues of potential concern.

For example, one question in the SF-36 asks 'How much of the time in the past 4 weeks- have you felt downhearted and blue?' If a subject responds 'most or all of the time', then the study coordinator should inform the study investigator.

Before completion

Subjects should be provided with the correct questionnaire at the appropriate visits and in the appropriate language.

Subjects should have adequate space and time to complete the forms

Subjects should be provided with a firm writing surface (such as a table or a clip board)

Questionnaire should be administered before the clinical examination

During completion

Administrator may clarify the questions but should not influence the response

Only one response for each question

Also see "Addressing Problems and Concerns"

After completion

Check for completeness and not for content*

Data should be sent from the eCRF / electronic device

Data should be reviewed by Investigator for AEs

*However, any response which may directly impact or reflect the subject's medical condition (e.g. noting of depression) should be communicated by the study coordinator to the investigator).

Addressing Problems and Concerns

Occasionally a subject may have concerns or questions about the questionnaires administered. Guidance related to some of the most common concerns and questions are given below.

The subject does not want to complete the questionnaire(s)

Tell the subject that completion of the questionnaire(s) is voluntary. The goal is to better understand the physical, mental and social health problems of subjects. Emphasize that such information is as important as any other medical information and that the questionnaire(s) is simple to complete. Suggest that the questionnaire(s) may be different from anything the respondent has filled in the past. If the subject still declines, retrieve the questionnaires. Record the reason for the decline and thank the subject.

The subject is too ill or weak to complete the questionnaire(s)

In these instances, the coordinator may obtain subject responses by reading out loud each question, followed by the corresponding response categories, and entering the subject's response. No help should be provided to the subject by any person other than the designated study coordinator. The coordinator should not influence subject responses. The study coordinator cannot translate the question into simpler language and has to be read verbatim.

The subject wants someone else to complete the questionnaire(s)

In no case should the coordinator or anyone other than the subject provide responses to the questions. Unless specified in the study protocol, proxy data are *not* an acceptable substitute for subject self-report. Subjects should be discouraged from asking a family member or friend for help in completing a questionnaire.

The subject does not want to finish completing the questionnaire(s)

If non-completion is a result of the subject having trouble understanding particular items, ask the subject to explain the difficulty. Re-read the question for them *verbatim* but do not rephrase the question. If the respondent is still unable to complete the questionnaire, accept it as incomplete. Thank the subject.

The subject is concerned that someone will look at his/her responses

Emphasize that all responses are to be kept confidential. Point out that their names do not appear anywhere on the questionnaire, so that their results will be linked with an ID number and not their name. Tell the subject that his/her answers will be pooled with other subjects' answers and that they will be analyzed as a group rather than as individuals. Tell the subject that completed forms are not routinely shared with treating staff and that their responses will only be seen by you (to check for completeness) and by the investigator. Any response which may directly impact on or reflect their medical condition (e.g. noting of severe depression) will be communicated by the coordinator to the physician.

The subject asks the meaning of a question/item

While completing the questionnaire, some subjects might ask the meaning of specific items so that they can better understand and respond. If this happens, assist the subject by rereading the question for them *verbatim*. If the subject asks to interpret the meaning of an item, do not try to explain it, but suggest that he/she use his/her own interpretation of the question. Subjects should answer the questions based on what *they* think the questions mean.

A General Information about all questionnaire(s):

All questionnaires have to be completed by the subjects in their local languages using an electronic device. The questionnaires should be completed by the subjects in a quiet area free from disturbance, and before any visit assessments. Subjects should receive no help from family members; if questions cannot be answered alone (due to problems with reading or understanding), then the doctor or nurse should read the questions and record the subject's responses without influencing their answers. The information provided is strictly confidential and will be treated as such. If a subject has missed a question or given more than one response per question, then this should be brought to subject. Incomplete questions should not be accepted without first encouraging the subject to complete unanswered questions.

The investigator must complete the subject/visit information on the electronic device and ensure that the center number, subject's number and initials are identical to the CRF. As there are no source data for this questionnaire, the data queries will be restricted to subject/visit information.
